8 Study Intervention

Study Medication

Study medication will be purchased by the BMC Investigational Pharmacy Service. Medication will be administered using a 250mcg/mL, 5mcg/dose, 60 doses/pen, 1.2mL prefilled pen. Subjects will receive either a 5 mcg dose of immediate release exenatide or a sham injection. The 5mcg dose of exenatide is approved as the first dose to be administered to patients at the start of their treatment with this drug for FDA-approved indications. The sham injection will be a needle stick insulin syringes with pre-affixed needles as a sham syringe. No fluid will be injected as a protection for maintaining the blind. Note that the volume of fluid injected for a 5mcg dose is only 0.02ml. We do not expect that subjects will sense this volume of fluid (or lack thereof) during the injection. Subjects will be shielded from seeing the injection to maintain the blind. The individual who administers medication will not participate in subject evaluation to maintain

The Effects of Exenatide, a GLP-1 Agonist, on Alcohol Self-Administration in Heavy Drinkers

Version 1.8 10.5.20

the study blind. The study medication will be administered subcutaneously 30 minutes prior to the priming dose of alcohol.

Dosing

Subjects will receive either a 5 mcg dose of immediate release exenatide or a sham injection on both alcohol challenge days.

Medication Storage

Medication will be stored in the Investigational Pharmacy under refrigerated conditions and may be stored at room temperature for up to 30-days following dispensing. Medication will be stored in a secured area until the time that medication is needed for study subjects. Stability and expiry will be monitored by IPS according to the labelling of the medication from the manufacturer.

Randomization

Study randomization will be performed by IPS using a stratified block randomization procedure. The study statistician will provide IPS with a randomization log. On the day of randomization, study staff will provide IPS with a randomization number based on the stratifying variable (heavy vs very heavy drinking) and IPS will determine the order of drug vs. sham exposure based on the randomization log.

Medication Labeling

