Study randomization: Subjects will be randomized to a crossover sequence of drug exposure. Subjects will be assigned to one of two groups, with one group receiving exenatide in the alcohol challenge Trial #1 and the other receiving exenatide prior in the alcohol challenge Trial #2. Randomization of subjects will be accomplished using a stratified randomization procedure that will allow for between-group balance for drinking status (heavy vs. very heavy). Heavy drinking is defined as ≥ 21 and < 35 standard drinks per week for men, and ≥ 14 and < 28 standard drinks per week for women. Very heavy drinking is defined as ≥ 35 standard drinks per week for men, and ≥ 28 standard drinks per week for women. This stratified randomization will minimize the possibility that the order of study drug administration seems to influence outcomes when order effects are actually related to differences in severity of drinking between the two groups of subjects who are receiving the study medication in a different order. On the day of randomization, subjects will undergo an alcohol breath test, urine drug screening, assessment of concomitant medications, and the TLFB. Subjects who have purposefully abstained from drinking and achieved 14 days of abstinence prior to the challenge will be discontinued from participation for ethical reasons⁴⁹.

Alcohol Challenge Trials 1 & 2: Subjects will return to the laboratory within 14 days of the baseline assessment to complete the alcohol Challenge Trial #1. Prior to the visit, subjects will complete a COVID-19 symptom screening questionnaire following standard of care procedures. If the subject does not complete the screening questionnaire before arriving in clinic, study staff will administer the questionnaire outside of the clinic at a 6-foot distance. If the subject answers 'yes' to any question about known COVID symptoms, their in-clinic visit will be cancelled and they will be advised to contact their PCP and/or get tested at a testing center. Concomitant medications, urine drug screening, Blood Alcohol Concentration (BAC) will be assessed to determine eligibility to proceed with the challenge. A BAC reading of 0.000 is required at each visit to continue with the study procedures. For safety reasons, subjects will be asked to arrange transportation plans that does not include driving themselves home.

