12.1 Study Hypotheses and Planned Analyses

For our primary outcomes, data from subjects who experience moderate to severe nausea during the alcohol self-administration trials will be excluded from our statistical analysis. Although the dosing chosen for this study minimizes the potential for nausea as a medication side effect, this may occur in some subjects. These subjects will be excluded from analyses as medication-induced nausea could confound the drinking outcomes. The presence of nausea will be established by a rating greater than 30 on a VAS scale that rates nausea from no nausea to unbearable nausea⁵³.

Hypothesis	Proposed Analyses
1. Subjects will consume less alcohol during an alcohol Challenge Trial when receiving exenatide	The volume of alcohol consumed during alcohol challenge trials 1 and 2 will be used to test the effect of exenatide on alcohol consumption. We will use a mixed

The Effects of Exenatide, a GLP-1 Agonist, on Alcohol Self-Administration in Heavy Drinkers
 Version 1.8 10.5.20

compared to when they receive a sham injection.	models repeated measures approach to test for differences between alcohol consumption between the exenatide and sham injection self-administration trials ⁵⁴⁻⁵⁵ . This data will be divided into first and second-hour blocks of self-administration. Within-subject factors for this analysis will include Treatment and Time Block. Trial order will be used as covariate in these analyses to allow evaluation as to whether the order of treatments had a significant effect on the outcome. Appropriate covariance structures will be determined using Akaike's information criteria to evaluate the best model fit. Results analysis will be examined for both treatment effects and the Treatment x Time Block interaction results.

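### The Hypothesis 1 and 2 models leave out the drinking-status stratum that randomisation uses to protect the order comparison, so a sequence test of order would be mildly conservative

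*Combined protocol and SAP*

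**What the plan says.** Section 8 (Randomization) states: "Study randomization will be performed by IPS using a stratified block randomization procedure". The stratifying variable is heavy versus very heavy drinking.

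Section 9 (Study randomization) gives one reason for stratifying: to avoid an apparent effect of order that in truth reflects "differences in severity of drinking between the two groups of subjects who are receiving the study medication in a different order". Order is thus described as a comparison between two groups of subjects, and drinking severity as something that could distort it.

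Section 12.1 sets out the models. For Hypothesis 1 (consumption): "Within-subject factors for this analysis will include Treatment and Time Block". The only covariate is trial order: "Trial order will be used as covariate in these analyses to allow evaluation as to whether the order of treatments had a significant effect". Hypothesis 2 (craving) has the same terms. Neither the stratum nor baseline drinking appears in any planned analysis.

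Section 12.2 powers only the within-subject treatment difference. It gives no power and no significance level for the order test.

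**The concern.** The design balances a factor that the protocol regards as related to outcome, and the analysis then ignores it. Balance lowers the true sampling variance of the sequence contrast. A model without the stratum leaves the severity variance in the between-subject error, so it does not recognise that gain. The reported standard error exceeds the true one, and the order test rejects less often than its nominal level.

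What is at stake is limited to that supporting test. Trial order is the only order assessment that the analysis plan names, and with 28 subjects a between-subject test is already weak. Omitting the stratum weakens it further, so a non-significant order result would mean even less.

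**Working it through.** **The plan's own figure.** Section 12.2 gives 28 completers, effect size 0.7, alpha 0.01 and power 0.81. For a paired t-test the noncentrality is 0.7 × √28 = 3.70 on 27 degrees of freedom. Two-sided power at 0.01 is 0.815, so the figure reproduces. (The unrounded ratio 1.5/2.1 = 0.714 gives 0.834.) This concerns treatment, a within-subject contrast, and does not depend on the stratum.

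**Inputs for the order test.**
- From Section 12.2: 36 randomised, 28 completers, SD of within-subject differences 2.1 drinks.
- Assumed, because the documents give no figure: residual intraclass correlation 0.5; strata 50:50; severity gap g of 1.0, 1.5 or 2.0 drinks; two-sided 5% level; true order effect 1.5 drinks; random attrition.

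**Variances.**
- Within-subject variance per session: 2.1²/2 = 2.205. An intraclass correlation of 0.5 makes the between-subject variance 2.205 as well.
- Variance of a subject's two-session mean within a stratum: 2.205 + 2.205/2 = 3.3075.
- Variance added by the stratum: g²/4 = 0.25, 0.5625 and 1.00.
- Share explained by the stratum: R² = (g²/4)/(3.3075 + g²/4) = 7%, 15% and 23%.

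**Perfect-balance bound (14 per sequence).** With the stratum in the model, the standard error is about √(3.3075 × 2/14) = 0.687. Without it, the model reports √((3.3075 + g²/4) × 2/14) = 0.713, 0.744 and 0.784. The ratio is 1/√(1 − R²) = 1.04, 1.08 and 1.14.

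**With attrition.** Dropout loosens the balance, so the overstatement shrinks. Simulated results with 28 of 36 analysed:

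| Gap (drinks) | R² | SE overstated | Rejection at nominal 5% | Power, stratum omitted | Power, stratum included |
|---|---|---|---|---|---|
| 1.0 | 7% | 2% | 4.6% | 0.52 | about 0.55 |
| 1.5 | 15% | 5% | 3.9% | 0.48 | about 0.55 |
| 2.0 | 23% | 11% | 3.1% | 0.44 | about 0.55 |

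A repeat run (20,000 trials per case, assumed blocks of 4) gave overstatement of 2%, 4–5% and 8–9%, and rejection of 4.4%, 3.9% and 3.4%. Power matched to within 0.01. The last row is therefore the least certain. With the stratum included, rejection returned to about 5%. At R² = 0 the two models performed alike.

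**Treatment contrast.** A mixed-model check used 28 subjects, a gap of 2 drinks, residual between-subject SD 1.5 and SD of differences 2.1. Adding the stratum lowered the sequence standard error from 0.779 to 0.675. The treatment and period standard errors stayed at 0.393, close to 2.1/√28 = 0.397. With 28 complete pairs plus 8 single sessions, the treatment standard error improves by at most about 0.6%.

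**The case against.** The strongest reply is that this touches only a nuisance test that the plan neither powers nor ties to any decision. Protection against order effects lies mainly in the design: randomised sequence, and a washout of 7 to 14 days against a stated terminal half-life of 2.4 hours. Even with the stratum, power for a 1.5-drink order effect is only about 0.55, so a null result reassures little either way. All of this stands, and it is why the point is of low priority.

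The effect also depends on coding. If trial order were entered as period (Trial 1 versus Trial 2), the contrast would be within subject and a stratum main effect would cancel. Section 12.1 speaks of the order of treatments, and Section 9 of groups treated in a different order. Both favour sequence, but neither defines the term.

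The largest gap is doubtful. Eight drinks at 0.0125 g/dl total 0.10 g/dl. Assuming 32–50 L of body water, blood that is 80% water and 14 g per standard drink, that is about 2.9–4.5 standard drinks. A 2.0-drink gap between strata would then be roughly 45–70% of everything on offer. The smaller gaps are more plausible.

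A reader might infer that the treatment result or the sample size is compromised, or that the order test raises too many false alarms. The documents support neither: treatment is a within-subject contrast, and the error in the order test is in the conservative direction.

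**Conclusion.** The mismatch is real but minor. The stratum that exists to protect the order comparison is absent from the Hypothesis 1 and 2 models. If trial order is the sequence group and severity predicts laboratory drinking, the order test is conservative to the extent tabulated above and loses about 0.03 to 0.11 of power for a 1.5-drink order effect. These sizes rest on an assumed correlation, stratum split, severity gap and random attrition. The nausea exclusion in Section 12.1 may loosen the balance further. Overstatement of 14% at the largest gap would need perfect balance in the analysed set, which 28 completers out of 36 do not guarantee.

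Two extensions might be inferred but do not follow. A stratum main effect would not yield treatment effects by severity group; that needs an interaction or separate fits. Nor does the argument reach Hypothesis 3, whose planned model names no order term.

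**What to change.** In Section 12.1, add the randomisation stratum (heavy versus very heavy, as used at randomisation) as a fixed between-subject factor in the Hypothesis 1 and 2 models, and state that trial order is the sequence group. This costs a sentence or two and one between-subject degree of freedom (26 to 25 for the order test with 28 subjects). No new data are needed, because the stratum is already recorded, and the sample size does not change. Priority: could be done, not essential.

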12.2 Sample Size Determination

A group size of 28 completers was selected for use in this study based on an assumed effect size of 0.7 suggested by similar alcohol self-administration studies with amount consumed as the primary outcome^{42,44}. This effect size is in the range we found for the anticonvulsant zonisamide used in a similar alcohol self-administration study⁴³. The sample size for this study is based on an estimated reduction of 1.5 standard drinks with an estimated standard deviation (2.1) of the between Challenge Trial differences in alcohol self-administration, with an effect size

The Effects of Exenatide, a GLP-1 Agonist, on Alcohol Self-Administration in Heavy Drinkers
Version 1.8 10.5.20

of this magnitude (i.e. 0.7). This requires a sample size of 28 to allow for detection of a significant within-subject difference in alcohol consumption with an alpha value of 0.01 and power value of 0.81. Based on an estimated 15-20% rate of non-completion for randomized subjects, we anticipate randomizing 36 subjects to achieve a sample of 28 completers. Given our experience with recruiting AUD populations into clinical trials, we expect a screening exclusion rate of roughly 50%. Approximately 72 subjects will be consented and screened in clinic to yield a sample of 36 eligible subjects.

Given that this a laboratory based experiment we do not plan to conduct any planned interim analyses in this study.

13 Ethics/Protection of Human Subjects

This study is to be conducted according to applicable US federal regulations and institutional policies (which are based in federal regulations, guidance, and ICH Good Clinical Practice guidelines).

This protocol and any amendments will be submitted to the Boston Medical Center and Boston University Medical Campus IRB, for formal approval of the study conduct. The decision of the IRB concerning the conduct of the study will be made in writing to the investigator. A copy of the initial IRB approval letter will be provided to the sponsor before commencement of this study.

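### Leaving the covariance structure of the primary alcohol-volume model to AIC, with no candidate list or degrees-of-freedom method, can let the nominal 1% treatment test run at about 1-3%

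*Combined protocol and SAP*

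**What the plan says.** The Hypothesis 1 row of the table in section 12.1 analyses alcohol volume by a repeated-measures mixed model. "Within-subject factors for this analysis will include Treatment and Time Block", so a completer contributes four values. Trial order is a covariate. The covariance rule is one sentence: "Appropriate covariance structures will be determined using Akaike's information criteria to evaluate the best model fit". No candidate structures, fallback, degrees-of-freedom method or robust standard error are named, and section 12.1 states no test level.

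Section 12.2 sizes the trial on a simpler quantity. "A group size of 28 completers was selected for use in this study", with "an estimated reduction of 1.5 standard drinks with an estimated standard deviation (2.1) of the between Challenge Trial differences in alcohol self-administration", "with an alpha value of 0.01 and power value of 0.81". This is a paired comparison of trial totals and involves no choice of covariance structure.

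**The concern.** The treatment effect contrasts one trial with the other, so its standard error depends on how much more alike two blocks of the same trial are than blocks of different trials. A higher within-trial correlation is plausible here. The two blocks are consecutive hours after one injection and one priming drink, whereas the other trial is 7-14 days away (section 9). Compound symmetry forces the two correlations to be equal. AR(1) treats the washout as if it were the same step as one hour to the next. If AIC selects such a structure when it is wrong, the model-based standard error is too small and the later test takes no account of the selection. What is at stake is the false-positive rate of the primary comparison, which the sample-size section sets at a strict 0.01.

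**Working it through.** **Inputs from section 12.2.** 28 completers; effect size 0.7 (1.5/2.1 = 0.714, rounded); alpha 0.01; power 0.81. **From section 12.1.** Four values per subject, trial order as covariate, AIC selection. **Assumed, because the documents give neither.** The within-trial correlation *w*, the between-trial correlation *b*, and the candidate lists.

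**1. The plan's own figure.** Paired t test, two-sided alpha 0.01, df 27: noncentrality 0.7 × √28 = 3.70 and power 0.815, which reproduces 0.81. Spending one degree of freedom on an order term (df 26) gives 0.813.

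**2. Why a simple structure misleads.** Take the difference between trials in mean volume per block, in units of a single block's variance.
- True variance: 1 + *w* − 2*b*.
- Compound symmetry uses one average correlation, (*w* + 2*b*)/3, and so targets 1 − (*w* + 2*b*)/3.
- True minus compound symmetry: 4(*w* − *b*)/3. The sign of *w* − *b* decides the direction of the error.

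| *w*, *b* | True | Compound symmetry | Ratio of standard errors |
|---|---|---|---|
| 0.5, 0.5 | 0.50 | 0.50 | 1.00 |
| 0.65, 0.5 | 0.65 | 0.45 | 0.83 |
| 0.6, 0.3 | 1.00 | 0.60 | 0.77 |
| 0.8, 0.5 | 0.80 | 0.40 | 0.71 |
| 0.4, 0.5 | 0.40 | 0.53 | 1.15 |

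**3. Why AIC may not rescue it.** Compound symmetry has 2 covariance parameters and unstructured has 10. Unstructured wins only if it improves −2 log-likelihood by more than 2 × (10 − 2) = 16. At *w* = 0.6, *b* = 0.3 and n = 28, AIC chose compound symmetry over unstructured in 53% of simulated data sets. With AR(1) also listed, it chose compound symmetry in 22% and AR(1) in 55%.

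**4. False-positive rate.** Simulation with no treatment effect, n = 28, normal complete data, REML, lowest AIC selected, and a two-sided 1% test with Satterthwaite degrees of freedom. There were 10,000-12,000 data sets per scenario (Monte Carlo standard error about 0.10-0.17 points). The rows below have equal variances and *w* above *b* (0.65-0.80 against 0.5, or 0.6 against 0.3), except the fixed unstructured row, which covers all scenarios.

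| Candidates | Rejections at nominal 1% |
|---|---|
| Compound symmetry, unstructured | 2.0-3.2% |
| Compound symmetry, AR(1), unstructured | 1.8-2.3% |
| Those three plus heterogeneous versions and Toeplitz | 1.9-2.4% |
| That list plus subject-by-trial random effect | 1.1-1.7% |
| Compound symmetry fixed, no AIC | 3.1-6.9% |
| Unstructured fixed, no AIC | 0.7-1.2% |

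**5. Where it does not inflate.** When compound symmetry is true, every list gave 0.7-1.2%. Unequal variances between treatments with equal correlations gave 1.0-1.1%. When *w* is below *b*, the selected test rejected about 0.5% of the time.

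**6. Degrees of freedom.** With df fixed at 26, the maximum fell to about 2.4% for compound symmetry and unstructured, and to 1.8% for the wider list without the subject-by-trial effect.

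**The case against.** The strongest reply is that the inflation comes from assumptions the plan does not make. No correlation is reported. The candidate list is open, and an analyst with two within-subject factors might well include a subject-by-trial effect, which brings the rate down to 1.1-1.7%. The direction is not certain either: hour-two drinking may fall after a heavy first hour, and each block is capped at four drinks, a bound the simulation ignores. AIC also did better than fixing compound symmetry outright. All of this stands, and it limits the claim to a conditional one.

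Four stronger readings are tempting, and the documents support none of them.
- A reader might infer that the 0.01 level is definitely not held. That requires *w* above *b* and a selected structure that ignores it. The 0.01 itself appears only in section 12.2.
- A reader might blame AIC as such. The cause is a misspecified structure combined with model-based standard errors.
- A reader might see a contradiction between sections 12.1 and 12.2. Sizing on a paired difference and analysing by mixed model are compatible, and an unstructured model gives the same treatment test when data are complete.
- A reader might extend the point to craving. The AIC sentence is in the Hypothesis 1 row only; the craving row states no such rule.

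What the reply does not remove is that error control for a primary outcome depends on a candidate list and a degrees-of-freedom method that the plan leaves open.

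**Conclusion.** The concern holds in conditional form. With about 28 subjects and within-trial correlation above between-trial correlation (0.6-0.8 against 0.3-0.5, assumed), the AIC rule lets a nominal 1% treatment test run at about 1-3%. The figure depends on the candidate list and the degrees-of-freedom method. It is about 1% if the correlations are equal and below 1% if the order is reversed, so no single inflated rate is a property of this plan. The calculation assumes normal, complete data. Section 12.1 also excludes subjects with nausea ratings above 30, so the analysed number may fall below 28; that effect is not quantified here. The point merits a change because a single pre-specified structure removes the dependence at almost no cost in power.

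**What to change.** Replace the AIC sentence for Hypothesis 1 with one pre-specified primary covariance: unstructured across the four trial-by-block values, with Kenward-Roger degrees of freedom and trial order in the model. Random effects for subject and subject-by-trial, fixed in advance, are an acceptable alternative. State the test level in section 12.1. Report AIC-chosen structures as sensitivity analyses only.

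For the treatment effect with complete data, the unstructured model matches the paired comparison of trial totals on which section 12.2 is sized. In simulation it rejected 0.7-1.2% at nominal 1%, which is 1% within simulation error. Power stays at 0.813-0.815 for an effect size of 0.7 and 28 completers. Unlike an analysis of trial totals alone, it still allows the planned Treatment by Time Block test.

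The cost is one paragraph of wording and a slightly wider confidence interval than a favourable AIC pick would give.
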